1. OBJECTIVES

1.1 Primary Objectives

Obtain preliminary data estimates of treatment compliance of radiation alone or chemoradiation (as defined by completion of initially prescribed radiotherapy and chemotherapy) in patients receiving beetroot (dietary nitrate/nitrite supplementation) and treatment for head and neck cancer

1.2 Secondary Objectives

- Quantify changes in strength, and body composition, before and following supplementation
- Determine feasibility of beetroot supplementation in head and neck cancer patients defined for each patient as the proportion of days successfully consumed supplement during treatment schedule
- Determine the toxicity of concentrated beetroot given in conjunction with radiation or chemo-radiation in SCCHN as measured by CTCAE v. 4.0
- Evaluate the trend in grade of mucositis during radiotherapy or chemoradiotherapy as measured weekly by CTCAE v 4.0
- Determine 1- and 2-year locoregional control rate and progression-free survival of subjects enrolled on this clinical trial.

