Beetroot will be self-administered daily (M-F) at the same time each day during the afternoon hours (12pm-5pm) and if possible, should be dosed after radiation to promote a consistent administration/habit. IDS will provide pre-measured 10g portions of the supplement powder each week during the IMRT period. The patient will mix and administer, and will record that they took the product daily in the compliance log that will be brought back and assessed at clinic. If at any point during the 7-week IMRT treatment the patient is unable to self-administer, the patient's family or study personnel who are recognized as clinical providers (such as a CRN) will mix the water and powder and will aid in supplement administration if the patient wishes to continue with the study. Subjects will then be discharged with beetroot for daily dosage (M-F) throughout the post IMRT follow-up period. Standard PEG tube care guidelines will be followed and the tube will be flushed with 30 to 50mL of water before and after every supplement dose. For patients requiring supplement administration assistance at IMRT discharge, a family member or caregiver of the patient will be identified and taught to provide assistance during the MP-EP follow-up period. An additional copy of the written mixing/administration instructions will be provided at this time and study staff will offer additional instructional assistance as needed.

Subjects who vomit the beetroot within the first 15 minutes after administration may repeat the administration once that same day. If vomiting occurs greater than 15 minutes after administration, the dose should not be repeated. Vomiting will be closely monitored and additional supplement packets will be provided at discharge in case of vomiting.

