Study volunteers will be asked to retain all used and unused study packaging on a weekly basis to turn in to study staff at the end of the week. Study packaging will be compared to the patient generated compliance log to document weekly compliance data. Subjects who are deemed "non-compliant" with the beetroot protocol (less than 3 consumed supplements during any 1 week period between baseline and midpoint measures) will be excluded in the per protocol analysis. Compliance to beet root consumption between midpoint and endpoint measure will be encouraged with weekly phone calls by nutrition graduate students supervised by [name]. [name] will oversee all aspects of the supplementation protocol. The Investigational Drug Service (IDS) at the University of Kentucky will assist with storage, supply management, quality control, and transfer of all beet root.

Bulleted supplementation administration guidelines for each study period are provided below: Baseline and prior to IMRT enrollment (supplement initiation period):

- Following randomization, participants will be taught to self-administer their supplement by study personnel.

- The CRA or nutrition student will then distribute the supplement needed for the 1-2 weeks prior to IMRT to the participant.
- The supplement powder will be packaged in 10g portions by the IDS. Packaging will only be identified by the letter “A” or “B” and only IDS staff will be unmasked to supplement assignment.
- Participants will begin daily, single dose supplementation (M-F during the afternoon hours) on the first day of receiving their supplement from study personnel.
- Participants will be taught to mix their assigned powder with 120mL of water and self-administer within 30 minutes of mixing.
- Compliance during this time period will be encouraged by phone calls, a supplement “count,” and with a patient generated supplement log sheet.

7-8 week IMRT treatment period (daily supplement observation period):

- Participants will be asked to continue daily (M-F) self-administration of the supplement. The pre-measured supplement powder will be provided to the participant on a weekly basis and patients will be asked to consume the supplement during the afternoon hours (M-F).
- At the beginning of treatment and throughout the IMRT period, study personnel will assess the need to provide additional education on proper self-administration of the study supplement (ex. Transitioning from PO feeding to enteral feeds).

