- CRNs serving as study personnel may offer observation or administration assistance if patient requests this and may document supplement compliance.
- Patients will be instructed to make up any missed doses by taking up to 1 additional dose per day on the weekend days. Patients will receive 5 doses per week (for M-F) and will be instructed to never exceed 1 dose per day.

4-6 weeks post-IMRT (discharge period):

- After completion of IMRT the participant will be instructed to continue daily (M-F) self-administration (PO or PEG) until completion of endpoint measures.
- For patients requiring supplement administration assistance at discharge, a family member or caregiver will be identified and taught to provide assistance.
- On the day of discharge and during scheduled follow-up visits, the CRA will distribute the pre-measured supplement packets needed for daily administration.
- Participants will continue to follow the supplement mixing protocol and be reminded to consume their assigned supplement within 30-minutes of mixing.
- Supplement compliance will continue to be encouraged by weekly phone calls by study personnel and compliance logs/supplement counts will occur at least twice per month.

Supplementation on Testing Days

On testing days, The BEETELITE™ solution (beet root) will be administered on-campus 20-45 minutes before subjects undergo the baseline, midpoint (following IMRT), and endpoint (4-6 weeks following midpoint) strength/endurance measures. Prior to testing, subjects will not have to refrain from standard oral care, using antibacterial mouth wash, or chewing gum 48 hours before testing sessions because the BEETELITE™ product does not rely on salivation/oral bacteria to convert dietary nitrate to nitrite (23). Previous studies have administered up to 500mL of beet root per day with nitrate concentrations of 5.5 mMol (24), 6.2mMol (7, 25), 5.2mMol (26), and 5.1mMol (27). Plasma nitrite (NO_2^-) levels in these aforementioned studies also increased following dietary nitrate supplementation.

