6. DOSING DELAYS/DOSE MODIFICATIONS

The following dosing delays and dose modifications refers only to adverse events which are at least possibly related to beetroot juice. When grade 3 and 4 toxicities are encountered and are possibly, probably or definitely related to beetroot juice, please use the following dose reduction table.

Event	Management/Next Dose for Beet Root
≤ Grade 1	No change.
Grade 2	No change

Event	Management/Next Dose for Beet Root
Grade 3 or 4	Hold until recovery to grade 2 or less, then decrease to Monday-Wednesday-Friday dosing

Exceptions to this procedure include: any grade alopecia and grade 3 or 4 fatigue.

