13. STATISTICAL CONSIDERATIONS

13.1 Study Design/Endpoints

This non-randomized, pilot study plans to enroll 35 total patients with previously untreated squamous cell cancer of the head and neck. As the goal of this study is to obtain preliminary data regarding current standard therapy compliance rates for this patient population at the University of Kentucky Markey Cancer Center and assess feasibility of an additional beet juice supplementation during therapy, the primary objective is to estimate treatment compliance defined as completion of radiation alone or radiation and chemotherapy with beet root supplementation during primary treatment. Treatment compliance is defined in more detail in section 5. Secondary objectives to obtain pilot estimates for cancer specific outcomes such as response rate, adverse events, mucositis rates, and 1 and 2 year locoregional control rates and progression-free rates Additional secondary

measures will include strength measures, CT scans, quality of life surveys, nitrate/nitrite levels, endurance testing, handgrip strength, and Body Composition DXA variables of interest (Bone Mineral Density, Bone Mineral Content, Area, % fat). Beet juice rates of completion will also be estimated to assess feasibility of this product.

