13.4.2 Evaluation of Outcomes

All patients included in the study will be assessed for treatment compliance, even if there are major protocol treatment deviations or if they are ineligible. All of the patients who met the eligibility criteria (with the possible exception of those who received no study medication) will be included in the intent to treat analysis for the primary completion endpoint as well as all secondary outcomes.

Due to concerns of potential non-compliance of taking all beet supplements over the course of primary treatment, a per protocol analysis will also be performed for all patients that consume at least 3 servings of the required beet supplements per week. Percentage of beet supplements taken will also be reported as part of this subgroup analysis.

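### Does the feasibility percentage need a written rule for weekend make-up, part and held doses?

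*Combined protocol and SAP*

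**What the plan says.** Section 1.2 defines feasibility of supplementation as "defined for each patient as the proportion of days successfully consumed supplement during treatment schedule". Section 13.1 counts it among the aims of the pilot, which is to "assess feasibility of an additional beet juice supplementation during therapy", and adds: "Beet juice rates of completion will also be estimated to assess feasibility of this product". Section 13.4.2, after describing the per-protocol analysis, says: "Percentage of beet supplements taken will also be reported as part of this subgroup analysis".

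The dosing rules behind these measures are in Sections 5.1.3 and 6. The schedule is: "Beetroot will be self-administered daily (M-F) at the same time each day during the afternoon hours". For missed doses: "Patients will be instructed to make up any missed doses by taking up to 1 additional dose per day on the weekend days". Five doses are supplied per week and no more than one is to be taken per day. After a grade 3 or 4 event at least possibly related to beetroot, the instruction is: "Hold until recovery to grade 2 or less, then decrease to Monday-Wednesday-Friday dosing".

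The per-protocol rule in Section 5.1.3 treats as non-compliant a subject with "less than 3 consumed supplements during any 1 week period between baseline and midpoint measures) will be excluded in the per protocol analysis". Section 13.4.2 words it as at least three servings of the required supplements per week.

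The weekly log in Appendix C has five numbered dose rows, each with a day, a time, the percentage consumed and the route. The monthly log in Appendix D has a column for every day, Saturday and Sunday included.

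**The concern.** Three sections describe what seems to be one measure in three ways: a proportion of days, a completion rate and a percentage of supplements taken. None gives a numerator or a denominator. Four choices are left open: whether a Saturday dose restores a missed weekday, whether held days and the Tuesday and Thursday doses dropped under Section 6 stay in the denominator, how a half-consumed dose counts, and which weeks make up the treatment schedule.

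The same question touches the per-protocol set, because a patient who obeys a hold of a full week has zero doses that week. Section 13.4.2 can also be read as reporting the percentage only in patients who already took at least three of five doses a week, which would build in a floor near 3/5 = 60%.

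Feasibility is part of what the pilot is for, and Section 13.2 says that the data will inform a larger study. If the analyst settled the rule after seeing the logs, the reported figure would depend on that choice, and a later team could not interpret it without knowing the rule.

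**Working it through.** The plan states no feasibility percentage, target or precision, so there is no figure to reproduce. The check counts doses under each reading and then asks which reading the documents favour. Miss and make-up rates are assumptions, because the documents give none.

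**1. One patient, make-up doses.** Seven weeks of radiotherapy give 7 × 5 = 35 planned weekdays. With two weekday misses a week, both made up:
- weekday doses only: 7 × 3 = 21, and 21/35 = 60%
- make-ups counted: 7 × (3 + 2) = 35, and 35/35 = 100%

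**2. Cohort mean, independent misses.** Let p be the chance that a weekday dose is taken, M ~ Binomial(5, 1 − p) the weekly misses, and u the chance that an available make-up is taken, with at most two per weekend. Mean intake with make-up = (5p + u·E[min(M, 2)])/5, where E[min(M, 2)] = 2 − 2P(M=0) − P(M=1).

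For p = 0.8: 2 − 2(0.32768) − 0.4096 = 0.93504. With u = p this gives 0.8 + 0.8 × 0.93504/5 = 0.9496.

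| p (no make-up) | E[min(M, 2)] | with make-up, u = p | with make-up, u = 0.5 |
|---|---|---|---|
| 70% | 1.30371 | 88.3% | 83.0% |
| 80% | 0.93504 | 95.0% | 89.4% |
| 90% | 0.49097 | 98.8% | 94.9% |

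The gaps are 18, 15 and 9 points with u = p, and 13, 9 and 5 points with u = 0.5.

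**3. Cohort mean, misses in whole weeks.** Illness would plausibly cluster misses. If a whole week is missed with probability 1 − p, at most two of its five doses can be recovered, so the gap is 2(1 − p)p/5:
- p = 0.7: 2 × 0.3 × 0.7/5 = 8.4 points
- p = 0.8: 2 × 0.2 × 0.8/5 = 6.4 points
- p = 0.9: 2 × 0.1 × 0.9/5 = 3.6 points

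If no doses are made up, the gap is 0.

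**4. Scale.** The 90% confidence half-width for a mean of 25 patients is 1.711 × SD/5, which is 3.4 points at an assumed SD of 10 and 6.8 at 20.

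**5. Held doses.** Take a hold for all of week k, then Monday-Wednesday-Friday, with every directed dose taken. Doses = 5(k − 1) + 3(7 − k):
- k = 1: 18/35 = 51.4%
- k = 3: 22/35 = 62.9%
- k = 7: 30/35 = 85.7%

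Against doses directed, each is 100%. One week-3 patient moves a mean of 25 by (1 − 22/35)/25 = 1.5 points.

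**6. What the documents favour.**
- *Unit.* With one dose per day, and a second allowed only to replace one vomited within 15 minutes, days with a dose and doses kept down are normally the same count.
- *Numerator.* The log's five rows leave the day open, so a Saturday dose takes one of the five. Section 5.1.3 also checks the log against returned packaging, which ignores the day of the week.
- *Denominator.* Five doses are supplied per week.
- *Window.* Section 5.1.3 labels the radiotherapy weeks as the supplement observation period, and Section 13.4.2 ties the concern about supplement intake to the primary treatment.
- *Population.* Section 1.2 defines the measure for each patient, and the intent-to-treat sentence in Section 13.4.2 covers all secondary outcomes.
- *Per-protocol rule.* Read as written in Section 5.1.3, it counts whatever was consumed in the week, weekends included, and gives a fully held week zero. Complete Monday-Wednesday-Friday dosing gives 3 and stays in.

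**The case for a change.** The best case for amending the plan is that feasibility is one of the two things the pilot sets out to learn, that at 70% or 80% weekday intake with independent misses the choice of rule moves the mean by more than its sampling error, and that one sentence written in advance would prevent a choice made after seeing the logs.

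Part of this stands. The three names for the measure do differ. No threshold is given for a successfully consumed dose although the log records part doses. The word required in Section 13.4.2 leaves open whether a Section 6 reduction changes what is required.

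The rest is weaker than it looks. The make-up question affects only patients who miss a dose and then take a make-up, not everyone who misses one. The larger gaps need independent misses. With clustered misses, only the 8.4 points at 70% intake exceeds the 6.8-point upper half-width. Holds need a grade 3 or 4 event at least possibly related to beetroot, and Section 7.1 calls adverse effects of beetroot rare. Leaving under-exposed patients out of a per-protocol set, whatever the reason, is ordinary practice. Choice after the fact is possible but not shown: Section 13.5 has the statistician involved in the case report forms and in a study-specific data management plan, where such counting rules normally sit.

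**Conclusion.** No change to the plan follows. This is missing detail that a sensible analyst fills by reporting doses taken over planned doses for all supplemented patients, with make-ups identified and holds listed. The logs record day and percentage consumed for each dose, so the figure with and without make-ups comes from data already collected. Only hold dates need a note.

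The size depends on assumptions. The gap between readings runs from 0 with no make-ups, through 3.6 to 8.4 points with clustered misses, to 9 to 18 points with independent misses made up as often as weekday doses are taken. Each patient with a week-3 hold adds about 1.5 points of difference. Those ranges rest on assumed weekday intake of 70% to 90% and a seven-week course.

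Nothing is decided on this figure. Section 13.3 describes the secondary endpoints as mainly descriptive and exploratory, no feasibility threshold or stopping rule uses supplement intake, and the primary treatment-compliance estimate in the intent-to-treat set does not depend on it. A clarifying sentence would be tidier, but no conclusion of the trial turns on it.

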2. BACKGROUND

2.1 Squamous Cell Carcinoma of the Head and Neck

Head and neck cancers are a group of geographically and biologically similar malignancies that originate in the upper aerodigestive tract, including the lip, oral cavity, nasal cavities, pharynx and larynx. The majority of these derives from the squamous mucosa, and often spread to regional lymph nodes of the neck, and subsequently to other distant sites. Head and neck cancer is strongly associated with tobacco exposure (both as smoking and chewing), alcohol consumption, and the human papillomavirus. Additional environmental exposures to various chemicals and dusts also predispose to head and neck cancer development, but are less common etiologies. These cancers are frequently aggressive in their biologic behavior, and some areas tend to present with more advanced disease, such as tumors which originate in the hypopharynx, as opposed to tonsillar or true vocal cord lesions, which tend to cause symptoms earlier in their course. Early-stage head and neck cancers have high cure rates with, though up to 50% of head and neck cancer patients present with advanced disease. As expected, cure rates decrease with more advanced disease cases, though patients with locally advanced disease, including those with regional nodal involvement, can still be cured with multimodality therapy. The most common regimen used in the setting of advanced disease is radiation 180 cGy of radiation given daily to a total dose of 6600 cGy to 7200 cGy with Cisplatin 100 mg/m² every three weeks although cetuximab weekly is also given in the setting. Multimodality chemoradiation is toxic and approximately 50% of subjects in multiple clinical trials by the RTOG complete the prescribed radiation within 50 days. In addition, only 67% of subjects receive all three planned doses of chemotherapy and this has been shown to impact overall survival and local control. Similarly patients receiving significant dose of radiotherapy to the oral mucosa suffers similar delays and compliance issues. Improving the tolerance of radiotherapy and chemoradiotherapy in head and neck cancer is an important avenue of investigation. Data from the American Cancer Society indicate that in 2012, an estimated 52,510 new cases of head and neck cancer will be diagnosed, of whom 10,500 patients will succumb to their disease (1).

2.2 Reducing Toxicity to Therapy

In head and neck cancer patients, compliance with combined modality treatment is essential to improve clinical outcomes. It is well known that compliance to treatment ranges from 50-70% and that the use of PEG tubes supports improved treatment compliance and outcomes by improving nutrient intake. Despite these findings, improved effectiveness has plateaued secondary to mucositis and side effects of multi-modal therapy including chronic fatigue, loss of muscle mass, and body fat. Various interventions have attempted to ameliorate the side effects of therapy in an effort to improve compliance. Medical therapies such as amifostine for radioprotection of normal tissue, and bezydamine, palifermin, and GCSF to reduce mucositis have not shown significant benefit.

2.3 Concentrated Beetroot

Novel dietary supplementation strategies, proven helpful in other human studies, coupled with enteral support may serve as an inexpensive method to improve medical compliance, physical function/body composition, and quality of life. Looking beyond standard macronutrient supplementation, beet root may offer an innovative solution to improve compliance because it has been implicated as an effective ergogenic aid by improving endurance and strength. Moreover, due to the metabolism of its bioactive components, may interrupt the pathogenesis of mucositis. Beet root is gaining attention in the sport performance arena due to recent reports that supplementation improves exercise capacity, increases muscle contractile efficiency, and may elicit other cardiovascular benefits secondary to mediating the nitrate-nitric oxide metabolic pathway. Dietary nitrate from beetroot has been shown to reduce the oxygen cost of exercise and enhance muscle contractile efficiency by reducing the use of phosphocreatine and ATP utilization (2). Improved exercise capacity has been demonstrated through delayed time to exhaustion (3, 4), improved time trial performance (5-7), and reduced oxygen cost of exercise (3, 5, 8-11). Enhanced mitochondrial efficiency has been shown as well (8, 12, 13). Due to these significant muscle-related physiological changes observed in healthy/nitrate-sufficient subjects, it is plausible that improvements in physical function in a sick population that is nitrate (exogenous) deplete will be observed and that the active ingredients may have a significant impact on lean tissue preservation directly and indirectly (via increased mobility/QOL). Concentrated beet root also contains a unique class of strong antioxidants, known as betalains, which have been shown to inhibit lipid peroxidation and heme decomposition. Recently, beetroot has shown some promising results in head and neck cancer patients. Roszkowski, 2012 (14) recently supplemented beetroot chips to patients undergoing radiotherapy in an effort to learn if antioxidants from beets would influence parameters of oxidative stress and DNA damage. Their results indicated that beetroot did not worsen survival time and reduced intensification of acute radiation reactions while not influencing markers of oxidative stress/DNA damage. The authors suggested that beetroot supplementation may be a safe method for assisting medical therapy.

Due to a direct correlation between compliance with medical therapy and improved clinical outcomes, there is a need to investigate promising interventions that may increase patient compliance with combined modality treatment, while concomitantly preserving muscle function and fat-free mass to further augment therapeutic gains.

